10.3.6.2. Subgroup Analyses

Subgroup analyses may be performed on selected outcomes in subgroups of interest. All subgroup analyses will be exploratory in nature. As the interest will be on how different treatment regimens work in a specific subgroup, instead of whether the treatment differences are the same across different subgroups, the subgroup analyses will be performed by analyzing the outcome data in different subgroups, instead of analyzing the outcome data in the whole population with subgroup factors included in the analyses model.

The following subgroups will be explored, and additional subgroups may be further explored if needed:

- baseline HbA1c (<8.4% and \geq 8.4%)
- baseline morning PPG (<13.5 mmol/L and \geq 13.5 mmol/L)
- baseline morning BG excursion (<4.4 mmol/L and \geq 4.4 mmol/L)
- baseline body mass index (BMI) (<25 and \geq 25)
- gender (male and female)
- 3-month persistence (discontinued insulin in the first 3 months of treatment or not)

Appendix 1. Abbreviations and Definitions

Term	Definition
AE	adverse event: Any untoward medical occurrence in a patient or clinical investigation subject administered a pharmaceutical product that does not necessarily have a causal relationship with this treatment. An adverse event can therefore be any unfavorable and unintended sign (including an abnormal laboratory finding), symptom, or disease temporally associated with the use of a medicinal (investigational) product, whether or not related to the medicinal (investigational) product.
ANCOVA	analysis of covariance
BG	blood glucose
BID	twice daily
BMI	body mass index
CIOMS	Council for International Organizations of Medical Sciences
complaint	A complaint is any written, electronic, or oral communication that alleges deficiencies related to the identity, quality, purity, durability, reliability, safety or effectiveness, or performance of a drug or drug delivery system.
CRF/eCRF	case report form/electronic case report form
CSR	clinical study report
enroll	The act of assigning a patient to a treatment. Patients who are enrolled in the trial are those who have been assigned to a treatment.
enter	Patients entered into a trial are those who sign the informed consent form directly or through their legally acceptable representatives.
ER	emergency room
ERB	ethical review board
FBG	fasting blood glucose
FPG	fasting plasma glucose
FSBG	finger stick blood glucose
GCP	good clinical practice

HbA1c	hemoglobin A1c
HCP	healthcare professional
IB	Investigator's Brochure
ICF	informed consent form
ICH	International Conference on Harmonisation
IDF	International Diabetes Federation
Investigational product	A pharmaceutical form of an active ingredient or placebo being tested or used as a reference in a clinical trial, including products already on the market when used or assembled (formulated or packaged) in a way different from the authorized form, or marketed products used for an unauthorized indication, or marketed products used to gain further information about the authorized form.
ITSQ	Insulin Treatment Satisfaction Questionnaire
IVRS/	interactive voice-response system
IWRS	interactive web-response system
MMRM	mixed-model repeated measures
NI	Non-inferiority
OAMs	oral antihyperglycemic medications
PCT	pragmatic clinical trial
PD	pharmacodynamic
PK	pharmacokinetic
PPG	post prandial glucose
PRO/ePRO	patient-reported outcomes/electronic patient-reported outcomes
QD	once daily
RCT	randomized clinical trial
SAE	serious adverse event
SAP	statistical analysis plan
SEITQ	Self-efficacy about Insulin Therapy Questionnaire
screen	The act of determining if an individual meets minimum requirements to become part of a pool of potential candidates for participation in a clinical study. BG measured by Self-Monitoring Blood Glucose Device

SUSARs	suspected unexpected serious adverse reactions
WHO	World Health Organization
T2DM	type 2 diabetes mellitus

A large, stylized logo consisting of the letters 'C', 'C', and 'I' in a bright red color. The letters are set against a solid black rectangular background that occupies the upper half of the page. The 'C's are thick and rounded, while the 'I' is a simple vertical bar.

Appendix 3. Study Governance Considerations

Appendix 3.1. Regulatory and Ethical Considerations, Including the Informed Consent Process

Appendix 3.1.1. Informed Consent

The investigator is responsible for ensuring:

- that the patient understands the potential risks and benefits of participating in the study
- that informed consent is given by each patient or legal representative. This includes obtaining the appropriate signatures and dates on the informed consent form (ICF) prior to the performance of any protocol procedures and prior to the administration of investigational products.
- answering any questions the patient may have throughout the study and sharing in a timely manner any new information that may be relevant to the patient's willingness to continue his or her participation in the trial.

Appendix 3.1.2. Ethical Review

The investigator or an appropriate local representative must give assurance that the ethical review board (ERB) was properly constituted and convened as required by International Conference on Harmonisation (ICH) guidelines and other applicable laws and regulations.

Documentation of ERB approval of the protocol and the ICF must be provided to Lilly before the study may begin at the investigative site(s). Lilly or its representatives must approve the ICF, including any changes made by the ERBs, before it is used at the investigative site(s). All ICFs must be compliant with the ICH guideline on Good Clinical Practice (GCP).

The study site's ERB(s) should be provided with the following:

- the current package inserts and updates during the course of the study
- informed consent form
- relevant curricula vitae

Appendix 3.1.3. Regulatory Considerations

This study will be conducted in accordance with:

- consensus ethics principles derived from international ethics guidelines, including the Declaration of Helsinki and Council for International Organizations of Medical Sciences (CIOMS) International Ethical Guidelines
- applicable ICH GCP Guidelines
- applicable laws and regulations

Some of the obligations of the sponsor will be assigned to a third-party.

Appendix 3.1.4. Investigator Information

Physicians who work in teaching or nonteaching hospitals with a specialty in endocrinology or internal medicine and over three years' experience initiating premix or basal insulin in type 2 diabetes mellitus (T2DM) patients, will be qualified to participate as investigators in this clinical trial.

Appendix 3.1.5. Protocol Signatures

The sponsor's responsible medical officer will approve the protocol, confirming that, to the best of his or her knowledge, the protocol accurately describes the planned design and conduct of the study.

After reading the protocol, each principal investigator will sign the protocol signature page and send a copy of the signed page to a Lilly representative.

Appendix 3.1.6. Final Report Signature

The clinical study report (CSR) coordinating investigator will sign the final CSR for this study, indicating agreement that, to the best of his or her knowledge, the report accurately describes the conduct and results of the study.

The sponsor's responsible medical officer and statistician will approve the final CSR for this study, confirming that, to the best of his or her knowledge, the report accurately describes the conduct and results of the study.

Appendix 3.2. Data Quality Assurance

To ensure accurate, complete, and reliable data, Lilly or its representatives will do the following:

- provide instructional material to the study sites, as appropriate
- sponsor start-up training to instruct the investigators and study coordinators. This training will give instruction on the protocol, the completion of the case report forms (CRFs), and study procedures.
- make periodic visits to the study site
- be available for consultation and stay in contact with the study site personnel by mail, telephone, and/or fax
- review and evaluate CRF data and use standard computer edits to detect errors in data collection
- conduct a quality review of the database

In addition, Lilly or its representatives will periodically check a sample of the patient data recorded against source documents at the study site. The study may be audited by Lilly or its representatives, and/or regulatory agencies at any time. Investigators will be given notice before an audit occurs.

The investigator will keep records of all original source data. This might include laboratory tests, medical records, and clinical notes. If requested, the investigator will provide the sponsor, applicable regulatory agencies, and applicable ERBs with direct access to original source documents.

Appendix 3.2.1. Data Capture System

An electronic data capture system will be used in this study. The site maintains a separate source for the data entered by the site into the sponsor-provided electronic data capture system.

Case report form data will be encoded and stored in electronic data capture system.

Any data for which paper documentation provided by the patient will serve as the source document will be identified and documented by each site in that site's study file. Paper documentation provided by the patient may include, for example, a paper diary to collect patient-reported outcome (PRO) measures (for example, a rating scale), a daily dosing schedule, or an event diary.

Appendix 3.3. Study and Site Closure

Appendix 3.3.1. Discontinuation of Study Sites

Study site participation may be discontinued if Lilly, the investigator, or the ERB of the study site judges it necessary for medical, safety, regulatory, or other reasons consistent with applicable laws, regulations, and GCP.

8.6. Interim Analyses20

9. REFERENCES21

10. APPENDICES22

Appendix 1: Definition of Exposure Interval22

1. GLOSSARY OF ABBREVIATIONS

Abbreviation or special term	Explanation
AE	Adverse Event
ANCOVA	Analysis of Covariance
BG	Blood glucose
D	Twice daily
BMI	Body Mass Index
CRF	Case Report Form
FBG	Fasting blood glucose
FPG	Fasting plasma glucose
FSBG	Finger stick blood glucose
HbA1c	Hemoglobin A1c
HCP	Healthcare professional
ITSQ	Insulin Treatment Satisfaction Questionnaire
MMRM	Mixed Model Repeated Measurements
NI	Non-inferiority
OAMs	Oral antihyperglycemic medications
PPG	Post prandial glucose
QD	Once daily
SAE	Serious adverse event
SEITQ	Self-efficacy about Insulin Therapy Questionnaire
TEAE	Treatment-emergent adverse event
TID	Three times a day
WHO	World health organization
T2DM	Type 2 diabetes mellitus

2. INTRODUCTION

The purpose of Study is to compare basal insulin analog once daily(QD) and insulin analog mid mixture twice daily (BID) as starter insulin regimen in Chinese patients with type 2 diabetes mellitus (T2DM) who have inadequate glycemic control with oral antihyperglycemic medications (OAMs) in real world settings. The table of contents and templates for the TFLs will be produced in a separate document.

3. STUDY OBJECTIVES AND ENDPOINTS

The objectives and endpoints of the study shows below:

Objectives	Endpoints
Primary	
1. To compare change in HbA1c from baseline to 24 weeks between insulin analog mid mixture BID and basal insulin analog QD treatments	1. The change in HbA1c from baseline to 24 weeks
Secondary	
2. To compare change in HbA1c from baseline to 48 weeks between insulin analog mid mixture BID and basal insulin analog QD treatments	2. The change in HbA1c from baseline to 48 weeks
3. To compare the proportion of patients who achieve HbA1c <7% at 24 and 48 weeks between insulin analog mid mixture BID and basal insulin analog QD treatments	3. Proportion of patients who achieve HbA1c <7% at 24 and 48 weeks
4. To compare the change in venous FPG from baseline to 24 and 48 weeks between insulin analog mid mixture BID and basal insulin analog QD treatments	4. Venous FPG change from baseline at 24 and 48 weeks
5. To compare the change in FSBG-based FBG and PPG from baseline to 24 and 48 weeks between insulin analog mid mixture BID and basal insulin analog QD treatments	5.FSBG-based FBG, PPG change from baseline at 24 and 48 weeks
6. To compare the daily insulin dose at 24 and 48 weeks between insulin analog mid mixture BID and	6. Daily insulin dose at 24 and 48 weeks

basal insulin analog QD treatments	
7. To compare the change in body weight from baseline to 24 and 48 weeks between insulin analog mid mixture BID and basal insulin analog QD treatments	7. Body weight change from baseline at 24 and 48 weeks
8. To compare the severe, nocturnal and total hypoglycemia incidences and rates during the 24-week and 48-week treatment period between insulin analog mid mixture BID and basal insulin analog QD treatments	8. The severe, nocturnal and total hypoglycemia incidences and rates during the 24-week and 48-week treatment period
9. To compare time to insulin treatment change between insulin analog mid mixture BID and basal insulin analog QD treatments	
9. Time to insulin treatment change: Defined as time to any of: insulin treatment discontinuation, switch, intensification or reduction in frequency
 
Discontinuation: Defined as stopping insulin treatment for 30 days or more.
 
Switch: Defined as stop the initial insulin therapy and started another insulin therapy of different class.
 
Intensification: Defined as any of the following: adding meal time insulin in basal insulin analog QD group; changing from BID to TID in insulin analog mid mixture BID group
 
Reduction in frequency: Defined as any of the following: changing from BID to QD; changing from TID to BID or QD

10. To compare the proportion of patients who achieve the HbA1c <7% without switching and discontinuing study insulin, and without using rescue therapy between insulin analog mid mixture BID and basal insulin analog QD treatments	10. Proportion of patients who achieve the HbA1c <7% without switching and discontinuing study insulin, and without using rescue therapy
11. To compare the patients-reported self-efficacy related to insulin therapy as assessed using SEITQ between insulin analog mid mixture BID and basal insulin analog QD treatments	11. The change in SEITQ score form baseline at 48 weeks

Tertiary/Exploratory	

12. To compare the insulin treatment pattern for
 
 • discontinuation • switch • intensification • reduction in frequency 
between insulin analog mid mixture BID and basal insulin analog QD treatments
	
12. Time to insulin discontinuation, switch, intensification or reduction in frequency
 
Proportion of patients who experience insulin discontinuation, switch, intensification or reduction in frequency during 48 weeks

13. To compare healthcare resource utilization (all-cause and T2DM-related; inpatient, outpatient and ER) between insulin analog mid mixture BID and basal insulin analog QD treatments
	
13. Healthcare resource utilization (all-cause and T2DM-related; inpatient, outpatient and ER) during 48 weeks


14. To compare patients' perception of insulin treatment satisfaction, as assessed using the ITSQ at 24 and 48 weeks between insulin analog mid mixture BID and basal insulin analog QD treatments
	
14. Domain and total ITSQ score at 24 and 48 weeks

15. To compare the patients-reported self-efficacy related to insulin therapy as assessed using SEITQ between insulin analog mid mixture BID and basal insulin analog QD treatments
	
15. The change in SEITQ score from baseline at 24 weeks

16. To compare the incidences and rates of other categories of hypoglycemia (documented symptomatic, asymptomatic, unspecified, probable symptomatic and relative hypoglycemia), if available, during the 24-week and 48-week treatment period between insulin analog mid mixture BID and basal insulin analog QD treatments
	
16. The incidences and rates of other categories of hypoglycemia (documented symptomatic, asymptomatic, unspecified, probable symptomatic and relative hypoglycemia), if available, during the 24-week and 48-week treatment period

4. SUMMARY OF STUDY DESIGN

Study F3Z-GH-IOQR (IOQR) is a multicenter, randomized, 48-week, parallel, 2-arm pragmatic trial in Chinese patients with T2DM who have failed to achieve adequate glycemic control with OAMs comparing the effectiveness of insulin analog mid mixture BID and basal insulin analog QD treatments in real world setting.

Approximately 830 participants will be randomized 1:1 into the 2 treatment groups such that there will be approximately 664 evaluable participants for primary analyses at Week 24. End of the trial is the date of the last visit or last scheduled procedure shown in the Schedule of Activities for the last patient.

5. SAMPLE SIZE DETERMINATION

The primary objective of the study will be evaluated using the classification method as proposed by Qu and colleagues (2011). With no prior hypothesis specified, the study will be considered a success if a conclusion may be reached by the classification method. With a 1:1 randomization ratio between insulin analog mid mixture BID and basal insulin analog QD, and assuming a non-inferiority margin of 0.4%, no treatment difference between mid mixture BID and basal insulin analog QD, and a common SD of 1.5% for the change from baseline in HbA1c at Week 24, 332 evaluable patients per arm will provide greater than 99% possibility for the study to reach a conclusion for primary analyses with 2-sided alpha level of 0.05. If we assume 20% of the patients will drop out without providing an evaluable post-baseline HbA1c, 415 patients per arm need to be randomized.

6. POPULATIONS FOR ANALYSES

For purposes of analysis, the following populations are defined:

6.1. Enrolled population

Enrolled population includes all participants who signed informed consent.

6.2. Randomized population

Randomized population includes all participants who were enrolled and who were randomized to any one of the treatment groups.

7. HANDLING OF MISSING DATA AND OUTLIERS

7.1. Handling of Missing Efficacy Data

The baseline value for efficacy measurements, which include HbA1c, FPG, FSBG-based FBG, PPG, BG excursion, daily insulin, body weight, SEITQ score, will be defined as the last non-missing observation on or before the randomization visit. If no data are available, the baseline value will be treated as missing. The last records within each window (Appendix 1) will be used for analyses for Week 24/Week 48.

7.2. Handling of Missing or Partial Date

Partial Dates for Adverse Events

- When only day is missing

- If it is the start date of an AE
 - If it occurs in a month before or after the month treatment started, the first day of the month will be used
 - If it occurs in the same month and year as the start of treatment
 - If the end date of the AE is prior to the start of study medication then the end date of the AE will be used
 - If the end date of the AE is missing or after the start of study medication then the date of the start of study medication will be used and the AE will be presumed to have started after the start of study medication
- If it is the end date of an AE, the last day of the month will be used.
- Only day and month are missing
 - If it is the start date of an AE
 - If it occurs in a year before or after the year treatment started then, January 1 of the year will be used
 - If it is occurred on the same year as the start of treatment, the date of the start of study medication will be used and the AE will be presumed to have started after the start of study medication.
 - If it is the end date of an AE, December 31 of the year will be used.

Partial Dates for Prior and Concomitant Therapy

- When only day is missing
 - If it is the start date of concomitant therapy then the first day of the month will be used
 - If it is the end date of concomitant therapy then the last day of the month will be used
- When day and month are missing
 - If it is the start date of concomitant therapy then January 1 of the year will be used
 - If it is the end date of concomitant therapy then December 31 of the year will be used

If the start date of concomitant therapy (including the imputed start date if applicable) is prior to the start of study medication or if the start date of concomitant therapy is missing then concomitant therapy will be classified as a prior medication.

If the end date of concomitant therapy (including the imputed end date, if applicable) is after the start of study medication or if the end date of concomitant therapy is missing then concomitant therapy will be classified as a concomitant medication.

Concomitant therapy may be classified as a prior medication, or a concomitant medication.

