Secondary Analyses: For change from baseline in venous fasting plasma glucose (FPG), finger stick blood glucose (FSBG)-based fasting blood glucose (FBG), post prandial glucose (PPG) and blood glucose (BG) excursion, the analyses model will be similar to the primary analyses model, except that the comparison will be based on the treatment contrast p-value from the ANCOVA model.

For percentages of patients reaching treatment goals (<7%) at Week 24 and Week 48, no missing data will be imputed. Count and percentages of patients reaching treatment goals will be summarized, and also be analyzed by a logistic regression model, with logit link function, treatment as fixed effect and baseline HbA1c as continuous covariate.

Insulin dose at each visit will be descriptively summarized by treatment groups by total daily dose (IU and IU/kg).

Safety: The incidence rate of case report form (CRF) collected severe, nocturnal and total hypoglycemic events will be summarized by visit and for the overall study duration. Pairwise comparison between treatment arms will be performed by Fisher's exact test. The overall yearly rates (events/patient/year) of those hypoglycemic events, calculated as, for each patient, the number of episodes times 365.25 and then divided by the patient's treatment duration, will be summarized, and analyzed by a negative-binomial regression model with treatment as fixed effects and log of (patient's treatment duration/365.25) as an offset variable.

Other Analyses: For the medial resource utilization and patient-reported outcome measurements summary statistics will be provided and comparison will be performed by appropriate general test.

Subgroup analysis will be performed for baseline HbA1c, baseline morning PPG, BG excursion, gender, and persistence levels in 2 treatment groups.

2. Schedule of Activities

Table IOQR.1. Schedule of Activities for Prospective Cohorts

eCRF Visit No.:	1	2	3	4	5	6	ET ^a
Week of treatment	0	4	12	24	36	48	ET
Visit Window (days)	–	±7	±7	±7	±14	±14	±14
Informed consent (before procedures/tests)	X						
Demographics	X						
Weight	X	X	X	X	X	X	X
Height	X						
Local urine pregnancy test ^b	X						
Duration of diabetes	X						
Anti-hyperglycemic medications(Non-insulin)	X	X	X	X	X	X	X
Insulin treatment ^c	X	X	X	X	X	X	X
Insulin dose ^d	X	X	X	X	X	X	X
Preexisting conditions/Adverse events ^e	X	X	X	X	X	X	X
Severe, nocturnal and total hypoglycemia events ^f	X	X	X	X	X	X	X

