8.4.1. Adverse Event

General AEs will be collected in this study. Count and frequency of AEs will be summarized for overall study population and by treatment arm. Also, AEs as a cause for insulin treatment change will be collected, and summarized by treatment arm. Serious adverse events will be collected and reported per Lilly standard operating procedure (SOP) and local regulatory requirement. Count and frequency of SAEs will be summarized by treatment arm.

Adverse events (AEs) and treatment-emergent adverse events (TEAEs) will be coded using the MedDRA dictionary. AEs and TEAEs will be categorized by system organ class and preferred term and will be presented. TEAEs are defined as AEs occurring during or after the initial dose of study drug. AEs documented prior to initial dose cannot be classified as TEAEs unless there is a worsening in severity during or after the initial dose of study drug. The overall incidence of TEAEs with all causalities will be summarized as the number and percentage subjects in each of the categories: TEAE, TEAEs leading to insulin treatment change, SAE.

The following summaries will be presented at both the subject (number [%] of subjects) and event (number of events) level:

- AEs by SOC, PT, and treatment
- Treatment-emergent AEs by SOC, PT, and treatment
- Treatment-emergent AEs by SOC, PT, maximum severity, and treatment
- SAE by SOC, PT, and treatment
- SAE related to study drug by SOC, PT, and treatment

- Treatment-emergent AEs leading to treatment insulin treatment change by SOC, PT, and treatment
- Treatment-emergent AEs related to study drug by SOC, PT, and treatment

For the incidence at the subject level by SOC and PT, if a subject experiences more than one event within the same SOC and PT, only one occurrence will be included in the incidence.

For the incidence at the subject level by SOC, PT, and severity, if a subject experiences more than one event within the same SOC and PT, only the most severe occurrence will be included in the incidence.

For the incidence at the subject level by SOC, PT, and relationship to investigational product, if a subject experiences more than one event within the same SOC and PT, only the most related occurrence will be included in the incidence.

For the summary of number of events, if a subject experiences more than one event within the same SOC and PT, all events will be counted.

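### SAP 7.2 drops the end-date check when an AE start is known only to the year, so an event that ended before first dose can be given a later start and counted as treatment-emergent

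*SAP*

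**What the plan says.** SAP 7.2 has two rules for AE start dates that could fall close to first dose.

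- **Only the day missing, same month and year as treatment start.** The end date is checked first: "If the end date of the AE is prior to the start of study medication then the end date of the AE will be used". Only if the end is missing or later is the start set to first dose.
- **Day and month missing, same year as treatment start.** There is no check: "If it is occurred on the same year as the start of treatment, the date of the start of study medication will be used". The event is then treated as having begun on treatment.

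Partial end dates move late. A missing day becomes the last day of the month, and for a missing day and month, "If it is the end date of an AE, December 31 of the year will be used".

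The imputed start feeds the safety tables through SAP 8.4.1: "TEAEs are defined as AEs occurring during or after the initial dose of study drug". The same section adds that an AE documented before the initial dose is not treatment-emergent unless its severity worsens at or after that dose.

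For anti-hyperglycemic therapy, partial start dates move early. With the day missing, "If it is the start date of concomitant therapy then the first day of the month will be used"; with day and month missing, "If it is the start date of concomitant therapy then January 1 of the year will be used". A therapy is labelled prior if the resulting start precedes first dose or if no start is recorded. A separate rule makes a therapy concomitant if its end date is after first dose or is missing.

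**The concern.** Imputing an unknown start to first dose is a reasonable conservative choice when nothing contradicts it. It is not reasonable when the recorded end date shows that the event was over before insulin began. The SAP accepts this in its day-missing rule and omits it from the year-only rule, where less is known about the start and the end date is the only evidence left.

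What is at stake is the accuracy of the treatment-emergent AE tables in SAP 8.4.1. An event that cannot have arisen on insulin could be tabulated as if it had. The record would also contradict itself, with a start later than its end.

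**Working it through.** The plan states no figure on this point, so there is none to reproduce. The check is to apply the SAP 7.2 rules literally to test dates. The documents give no calendar dates; first dose on 15 June 2017 is an assumption for illustration.

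**AE rule**

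| Start recorded | End recorded (end used) | Start as written | Start after end? | Start with the check copied in |
|---|---|---|---|---|
| 2017 | 10 Jun 2017 | 15 Jun | yes, by 5 days | 10 Jun, before first dose |
| 2017 | Mar 2017 (31 Mar) | 15 Jun | yes | 31 Mar, before first dose |
| 2017 | 2017 (31 Dec) | 15 Jun | no | 15 Jun, unchanged |
| 2017 | missing | 15 Jun | not applicable | 15 Jun, unchanged |
| Jun 2017 | 10 Jun 2017 | 10 Jun | no | 10 Jun, unchanged |

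The first and last rows have the same end date and the same first dose. They differ only in whether the start month was recorded, yet one is placed on treatment and the other before it.

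The result does not depend on the chosen date. Take first dose on every seventh day of a 365-day year, starting on 1 January, and every possible end date before it in that year. That is 7 × (0 + 1 + … + 52) = 7 × 1,378 = 9,646 combinations. In all 9,646 the imputed start is later than the end and on or after first dose. This shows that the rule fails whenever its conditions are met. It says nothing about how often they are met.

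**Conditions for a wrong count**

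1. The start is known only to the year, and that is the year of first dose.
2. The end is known to the day and precedes first dose, or is known to a month before the first-dose month. An end known only to the first-dose month becomes the last day of that month, so it cannot precede first dose. A missing or year-only end does not trigger the fault either.
3. The AE was first documented after first dose. Otherwise the SAP 8.4.1 exclusion applies unless the event worsens.

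**How often they could be met.** Protocol 9.2 has AEs recorded once consent is signed. Consent and randomization are both at Visit 1 (Protocol 2 and 7.2). The event must therefore fit between consent and first dose. The length of that interval is not given. It need not be zero: the study supplies no drug (Protocol 7.1), and Protocol 9.2.1 provides for serious events between consent and first use of the product.

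**Therapy rule**

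Keep first dose at 15 June 2017 and take an oral drug that is ongoing:

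- Added 20 June, day missing: start becomes 1 June, labelled prior and also concomitant.
- Added 20 August, day missing: start becomes 1 August, labelled concomitant only.
- Added 20 August, year only: start becomes 1 January, labelled prior and also concomitant.

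Over 9,700 test combinations of a first-dose date from 2 January onward, a later add-on date in the same year recorded by year only, and an end that was missing or later than the add-on, all 9,700 met the prior rule and all 9,700 met the concomitant rule. This follows from the rules: a drug added after first dose must end after first dose or have no end date.

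**The case against.** The strongest case against is that the fault has little to act on, and much of it stands.

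- **SAP 8.4.1 already excludes some of these events.** An AE documented before the first dose is kept out of the treatment-emergent tables whatever start is imputed. This stands, so a reader who infers that every affected record is misclassified goes too far. It does not cover an event first reported at a later visit.
- **The interval is short.** Consent and randomization share a visit, and few patients will have an AE that begins and ends before first dose with a start known only to the year. This stands on likelihood, although the documents do not give the interval.
- **Preexisting conditions.** The Protocol 2 schedule has one row for "Preexisting conditions/Adverse events", and a reader might infer that old conditions with vague onset dates would flood the tables. The documents do not support this. Protocol 9.2 records preexisting conditions as such and makes only changes and new conditions AEs, and SAP 8.1.2 summarizes medical history separately.
- **Negative duration.** A start after the end implies one, but SAP 8.4.1 plans counts and incidences, not durations. The inconsistency signals the fault and has no analysis consequence of its own.
- **Hidden add-on therapy.** Anti-hyperglycemic drugs are the only concomitant therapy collected (Protocol 7.7), so a reader might infer that back-dating hides a co-treatment difference between arms. It does not follow, because every such add-on also meets the concomitant rule. Nor does SAP 8.1.3 tie its baseline summary to the prior label.

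**Conclusion.** The point holds for the AE rule and is minor. In the year-only rule of SAP 7.2, an AE whose known end, or end month, precedes first dose receives a start after its end and is presumed to have begun on treatment. If it was first documented after first dose, it is wrongly counted as treatment-emergent.

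The number of such records cannot be derived from the documents and is probably small. That judgement rests on AE recording starting at consent and on first dose following Visit 1 fairly soon; the second is an assumption. The primary and secondary efficacy analyses are not shown to depend on these dates.

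For therapy, the only remaining point is that a partial start date can add a false prior label to a drug that is also classed as concomitant. SAP 7.2 does not say clearly whether both labels may apply.

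**What to change.** In SAP 7.2, add to the rule for a missing day and month in the treatment-start year the line already used for a missing day: "If the end date of the AE is prior to the start of study medication then the end date of the AE will be used". State that such an AE is not flagged as treatment-emergent. Leave the imputation to first dose in place for ends that are missing or on or after first dose.

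For therapy, add one sentence on whether a drug may be both prior and concomitant, so that a false prior label is not read as baseline use.

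The cost is one line for AEs and one for therapy, with the matching programming. No new data are needed, and the efficacy analyses do not change.
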